6.4 Study Discontinuation and Stopping Criteria

6.4.1 Dose Escalation Stopping Criteria

Dose escalation will be stopped if one of the following conditions apply:

• Death of a subject (AE grade 5 toxicity) in one cohort, at any time, that is considered related to the IP, judged by the Investigator

- One subject in a cohort develops an AE ≥ Grade 3 toxicity, that is considered related to the IP, judged by the Investigator
- One subject in a cohort develops an AE Grade 2 toxicity that persists for more than 7 days and is considered related to the IP, judged by the Investigator
- 2 or more of the subjects in a cohort have experienced severe adverse events, judged to be possibly or probably related to the IP, judged by the Investigator;
- 2 or more subjects receiving HM15211 develop similar clinically significant laboratory, significant ECG or vital signs abnormalities, or severe AEs in the same organ class, indicating dose-limiting intolerance. Dose escalation may proceed if after review of the data by the Investigator and discussion with Sponsor, it is concluded that the events are not drug related;
- It is determined that the limit of safety and/or tolerability has been reached. Decision will be made between Sponsor and Investigator.

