human chorionic gonadotropin (hCG)performed at Screening. Follicle-stimulating hormone (FSH) test for postmenopausal women (defined as amenorrheic female subjects <60 years of age and not surgically sterile) at Screening. Urine pregnancy testing via commercial kit at CRU will be performed at timepoints stated in the Schedule of Events. Urine pregnancy testing may be performed per Investigator's discretion at additional timepoints during the study, if there is reason to believe the subject might be pregnant.

- (a) Microscopic analysis should be performed only if urine evaluations are abnormal.
- (b) In the event of abnormal TSH, Free T3/T4 may be collected at Investigator discretion.

The local laboratory will perform all necessary laboratory tests listed above. The results of laboratory tests will be sent to the Investigator or designee, who is responsible for reviewing these results. All laboratory safety data will be faxed or transferred electronically.

Laboratory reports must be signed and dated by the Investigator or designee indicating that the report has been reviewed and any abnormalities have been assessed for clinical significance.

All clinically significant laboratory abnormalities must be recorded as an AE. A clinically significant laboratory abnormality may be verified by retesting and may be followed upon discretion of the Investigator.

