10.2 Severity of AEs

The different categories of intensity (severity) are characterized as follows:

Mild: The event is transient, easily tolerated by the subject and does not

affect the subject's daily activities.

Moderate: The event causes the subject discomfort and interrupts the subject's

usual daily activities.

Severe: The event is incapacitating and causes considerable interference with

the subject's usual activities.

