10.3 Relationship to Study Treatment

The relationship of each AE to the study drug(s) will be assessed by the Investigator or Sub-Investigator on the basis of his/her clinical judgment and the following definitions:

1= Related:

The AE follows a reasonable temporal sequence from the study product administration, and cannot be reasonably explained by the subject's clinical state or other factors (e.g., disease under study, concurrent diseases, or concomitant medications).

The AE follows a reasonable temporal sequence from the investigational product administration, and represents a known reaction to the drug under study or other drugs in its class, or is predicted by the known pharmacological properties of the drug.

The AE resolves with discontinuation of the investigational product and/or recurs with rechallenge, if applicable.

2 = Not Related:

The AE does not follow a reasonable temporal sequence from investigational product administration, or can be reasonably explained by the subject's clinical state or other factors (e.g., disease under study, concurrent diseases, and concomitant medications).

3= Not Assessable/ Not Classifiable:

The AE cannot be judged because of insufficient or contradictory information. The AE cannot be supplemented or verified.

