10.4 Procedures

10.4.1 Collection and Recording of AEs

Collection of all AEs (serious AEs and non-serious AEs) will commence from the time the subject signs the informed consent to participate in the study until the post-treatment follow-up visit. Throughout the in-house treatment period, the Investigator will assess whether any subjective AEs have occurred. In order to avoid bias in eliciting AEs, a non-specific question, such as "How have you been feeling since your last visit?" may be asked. Subjects may report AEs occurring at any other time during the study.

All subjects experiencing AEs, whether considered associated with the use of the study medication or not, must be monitored and given appropriate medical treatment at the discretion and judgement of the Investigator until the symptoms subside and any clinically relevant changes in laboratory values have returned to baseline or until there is a satisfactory explanation for the changes observed. All AEs will be documented in the AE page of the CRF, whether or not the Investigator concludes that the event is related to the drug treatment. The event term, start and stop dates, severity, action taken with study drug and outcome, will be documented, along with the Investigator's opinion of the causal relationship between the event and the study drug.

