10.6 Follow-up of AEs and SAEs

All AEs should be followed up and subjects will be rendered appropriate medical care and treatment at the discretion of the Investigator until resolution or until the Investigator and Sponsor concludes that "further follow-up is not necessary". If the AE has not resolved by the post-treatment follow-up visit, the stop date will be recorded as "ongoing."

All SAEs should be followed up until resolution or permanent outcome of the event or until the Investigator and Sponsor judge that further follow-up is not necessary.

If information is not available at the time of the first report and becomes available later, the Investigator should complete a follow-up SAE form at the earliest possible or provide other written documentation and fax it immediately within 24 hours of receipt of information to the Sponsor or designee. Copies of any relevant data from the hospital notes (e.g., ECGs, laboratory tests, discharge summary, postmortem results) should be sent accordingly.

All other non-serious AEs must be followed until the outcome of the event is "recovering" (for chronic conditions), or "recovered", or until the end of the post-treatment follow-up stated in the protocol, whichever comes first, and until all queries related to these AE's have been resolved.

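### The dose-escalation stopping criteria in 6.4.1 use toxicity grades and causality terms that the adverse event scales in 10.2 and 10.3 cannot supply

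*Protocol*

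**What the plan says.** Protocol 6.4.1 lists conditions, any one of which stops escalation. In order:

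- Criterion 1: a related death, labelled grade 5.
- Criterion 2: one subject with a related event of Grade 3 or higher.
- Criterion 3: one subject who "develops an AE Grade 2 toxicity that persists for more than 7 days", again related.
- Criterion 4: "2 or more of the subjects in a cohort have experienced severe adverse events, judged to be possibly or probably related to the IP".
- Criterion 5: two or more HM15211 subjects with similar clinically significant laboratory, ECG or vital-sign abnormalities, or with severe events in the same organ class.
- Last: a discretionary stop by sponsor and investigator at the limit of safety or tolerability.

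The adverse event chapter uses other terms. Section 10.2 opens with "The different categories of intensity (severity) are characterized as follows" and then gives three levels, mild, moderate and severe, each described by its effect on daily activities. Section 10.3 has Related, Not Related and "3= Not Assessable/ Not Classifiable". Section 10.4.1 fixes what is captured: "The event term, start and stop dates, severity, action taken with study drug and outcome, will be documented", together with the investigator's causality opinion. On laboratory findings, 9.1.8 says "All clinically significant laboratory abnormalities must be recorded as an AE", and 10.1.3 reserves the term laboratory AE for abnormalities that need active management.

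Section 4.5 allows the escalation decision once at least six subjects, four of them on active drug, have completed at least Day 10.

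**The concern.** These criteria decide whether a first-in-human trial may go to as much as twice the dose. They have to be applied to the AE record that the protocol prescribes, and that record has no numeric grade and no possible or probable tier. At the meeting, someone must convert moderate or severe into Grade 2 or Grade 3, and must decide whether an event counts as possibly related, with no stated conversion. Two careful people could read the same AE page and reach opposite decisions on criterion 2 or 3, each of which a single subject can trigger.

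The 7-day persistence test in criterion 3 also sits close to the Day 10 review, so its outcome may not yet be known when the decision is made.

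**Working it through.** **Severity.** The terms compare as follows.

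| Item in 6.4.1 | Term needed | Available from 10.2 / 10.4.1 |
|---|---|---|
| Criterion 1 | Grade 5 | Death itself; no scale needed in practice |
| Criterion 2 | Grade 3 or higher | Mild / moderate / severe only |
| Criterion 3 | Grade 2 | Mild / moderate / severe only |
| Criteria 4 and 5 | Severe | Severe, defined |

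No grading scale is named in the body, the abbreviations or the references, and no mapping from grades to levels is given. The mismatch therefore bites on criteria 2 and 3.

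Take one subject with an asymptomatic, clinically significant laboratory abnormality that needs active management. Sections 9.1.8 and 10.1.3 make it an AE. It does not interrupt daily activities, so it is neither moderate nor severe under 10.2, whatever numeric grade a toxicity scale would give. If it persists, it is not clearly mild either, because 10.2 describes mild events as transient. Criterion 5 reaches laboratory abnormalities without a grade, but only when they are similar in two or more HM15211 subjects. The single-subject case falls to criteria 2 and 3, which the recorded severity cannot settle.

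**Causality.** Criteria 1 to 3 use related, which 10.3 defines. Criterion 4 uses possibly or probably, which 10.3 does not. No text says how Not Assessable counts.

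**Criterion 2 against criterion 4.** If severe means Grade 3 or higher and possibly/probably means Related, every case that meets criterion 4 (two subjects) has already met criterion 2 (one subject). If a lower causality tier was meant, 10.3 cannot record it.

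The one-subject threshold should survive any tidying. With 6 active subjects and an assumed event probability p (not a protocol figure):

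- P(at least 1) = 1 − (1 − p)^6
- P(at least 2) = 1 − (1 − p)^6 − 6p(1 − p)^5

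| Assumed p | At least 1 | At least 2 |
|---|---|---|
| 10% | 0.47 | 0.11 |
| 20% | 0.74 | 0.34 |
| 30% | 0.88 | 0.58 |

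**Timing of criterion 3.** Day 10 is 216 h after the subject's own dose (9.1.6). The ±1 day window gives 192 to 240 h. More than 7 days means more than 168 h. Expected Cmax is at about 3 days, or 72 h (6.3).

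To meet criterion 3 at the visit, onset must come before (visit time − 168 h):

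- 192 − 168 = 24 h
- 216 − 168 = 48 h
- 240 − 168 = 72 h

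An event starting at 72 h has lasted 192 − 72 = 120 h, 216 − 72 = 144 h or 240 − 72 = 168 h at these visits. It exceeds 168 h at none of them.

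Next, the earliest dosing of the next cohort, assuming decision and check-in both on the nominal Day 10 visit day. Day -2 to Day 1 is 48 h, so the first dose is at 216 + 48 = 264 h. By then, onsets up to 264 − 168 = 96 h have reached 7 days. The sentinel rule in 6.1 holds the rest of that cohort for at least another 24 h, to 288 h, by when onsets up to 288 − 168 = 120 h have reached 7 days.

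**The case against.** The best defence is that the criteria assign most judgements to the investigator, who can grade an event at the meeting, and that criterion 5 already covers laboratory findings without grades. That answers the case of similar abnormalities in two or more HM15211 subjects. It does not answer the single-subject case, and judgement without a named scale is exactly what leaves criteria 2 and 3 open to different readings. It is fair to add that a persistent laboratory abnormality does not default to mild. But that leaves it with no clear category, which is no better.

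Three stronger readings are tempting, and the protocol does not support them.

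- *A reader might infer that a related Grade 2 event still running at Day 10 escapes the rules.* It does not in general. With onset before 48 h and still present at 216 h, it already meets criterion 3. Section 6.4.1 has no Day 10 cut-off, so an event that passes 7 days after the meeting still meets the criterion. The last bullet also allows a discretionary stop, and sentinel dosing limits early exposure in the next cohort. Only a narrow timing gap remains, and its width rests on the assumed same-day decision and check-in.
- *A reader might infer that it is unclear whether the one-subject or the two-subject threshold governs.* Any one criterion suffices, so the stricter governs, and criterion 4 is at worst redundant.
- *A reader might infer that laboratory events go unchecked because the routine panel is not drawn on Day 10.* Section 9.1.8 permits retesting. Under 10.4.1, subjects with AEs "must be monitored and given appropriate medical treatment at the discretion and judgement of the Investigator until the symptoms subside" and until clinically relevant laboratory changes return to baseline or are explained. Section 10.6 adds: "All AEs should be followed up and subjects will be rendered appropriate medical care".

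The sponsor's choice of Day 10, on the ground that dose-limiting events occur around Cmax, is deliberate and is not disputed here.

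**Conclusion.** The point holds as a mismatch within the protocol. Criteria 2 and 3 need grades that the AE record does not hold, and criterion 4 needs a causality tier that 10.3 does not have. A manual or analysis plan not at hand might name a scale, but the stopping rules and the AE definitions are both fixed in the protocol and disagree there. It should be fixed, because the rules gate increases of up to 2-fold in a first-in-human trial.

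The size cannot be put as an error rate. The probabilities above rest on assumed event rates and show only that one-subject and two-subject thresholds behave very differently in six active subjects.

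The timing point is secondary. At a nominal Day 10 review it concerns related Grade 2 events with onset from 48 h. Under the same-day assumption, by the next cohort's first dose it has shrunk to onsets after 96 h.

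**What to change.** - **Severity.** Use one scale in 6.4.1 and 10.2. Either name a numeric scale and record the grade on the AE page, or restate criteria 2 and 3 as severe and moderate with an explicit rule for laboratory events.
- **Causality.** Restate criterion 4 in the 10.3 categories. Say that Not Assessable counts as related for stopping, or state how else it counts.
- **Threshold.** Keep one subject as the trigger for a related severe or Grade 3 or higher event. Delete criterion 4 if it then adds nothing.
- **Timing.** State that criterion 3 is rechecked before the next cohort's first dose, and that dosing waits until an ongoing related Grade 2 event resolves or passes 7 days, which stops escalation. For onset at 72 h the wait ends just after 72 + 168 = 240 h (Day 11). For onset at 144 h it ends just after 144 + 168 = 312 h (Day 14).

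The cost is protocol wording, one extra AE-page field if the numeric scale is chosen, and an occasional delay of a few days between cohorts.

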6.4.2 Criteria for Early Termination of the Study

The study will be completed as planned unless one or more of the following criteria are satisfied

- violation of Good Clinical Practice (GCP) that compromises the ability to achieve the primary study objectives or compromises subject safety.
- Failure to meet expected enrollment goals
- Administrative Reasons

In case that the Sponsor, an institutional review board (IRB)/ independent ethics committee (IEC), or regulatory authority elects to terminate or suspend the study or the participation of an investigational site, a study-specific procedure for early termination or suspension will be provided by the Sponsor; the procedure will be followed by applicable investigational sites during the course of termination or study suspension.

6.4.3 Criteria for Early Termination of Individual Subjects

Subjects may withdraw their consent to participate in the study at any time.

If a subject withdraws consent, the date and reason for consent withdrawal should be documented. Subjects will be encouraged to remain in the clinic for safety assessments until the Investigator deems that it is safe for the subject to be discharged. Subject data will be included in the analysis up to the date of the consent withdrawal.

- AE or SAE that requires discontinuation at the discretion of the Investigator
- Protocol violation: If protocol violation or concurrent illness occurs, which, in the clinical judgment of the Investigator or after discussion with the Sponsor, may

invalidate the study by interfering pharmacokinetically or pharmacodynamically with the investigational products, subject will be withdrawn by the Investigator.

- Lost to follow-up. The subject did not return to the clinic and attempts to contact the subject were unsuccessful. Attempts to contact the subject must be documented.
- Voluntary withdrawal of consent (mandatory removal from study)
- Discretion of Investigator (document reason on CRF)
- Subject becomes pregnant or begins breastfeeding (mandatory)
- Study discontinuation by Sponsor

Wherever possible, the tests and evaluations, including those listed for the Follow-up Visit should be performed for all subjects who discontinue prior to the completion of the study.

In the event the Investigator determines to terminate a subject participation in the Clinical Study, the Investigator must notify the Sponsor of such decision and rationale immediately in writing. In all cases, the appropriate IRB/IEC and other applicable regulatory authorities shall be informed.

7.0 STUDY POPULATION

7.1 Inclusion Criteria

Subjects who meet all criteria at Screening will be included in the study:

- 1. Male and female subjects.
- 2. Age \geq 18 to \leq 65 years.
- 3. Body mass index (BMI) \geq 30 to \leq 40 kg/m², with stable body weight by history for 3 months (defined as change < 5%).
- 4. HbA1c < 6.5 %.
- 5. Female subjects must be non-pregnant and non-lactating. Females of child bearing potential must use highly effective contraceptive methods, stable at least 2 months prior to the screening. Male subjects must be surgically sterile, abstinent or if engaged in sexual relations of child-bearing potential, the subject and his partner must use an acceptable method of contraception.
- 6. Ability to provide written informed consent.

7.2 Exclusion Criteria

Subjects who meet any of the following criteria will be excluded from the study:

- Previous surgical treatment for obesity (bariatric surgery, gastric banding etc.) or any other gastrointestinal surgery that may induce malabsorption, history of bowel resection >20 cm, any malabsorption disorder, severe gastroparesis, any GI procedure for weight loss (including LAP-BAND®), as well as clinically significant gastrointestinal disorders (e.g. peptic ulcers, severe GERD) at Screening.
- 2. Use of antacids, anticoagulants, drugs that directly modify gastrointestinal (GI) motility, including, but not limited to, anticholinergics, antispasmodics, 5HT3 antagonists, dopamine antagonists, or opiates within 2 weeks of screening.
- 3. Uncontrolled hypertension, defined as systolic blood pressure >150 mmHg and/or diastolic blood pressure ≥ 100 mmHg at screening (reading may be repeated on a different day). (Subjects with uncontrolled hypertension may be rescreened after 3 months, following initiation or adjustment of antihypertensive therapy).
- 4. Use of any drugs that are known to interfere with glucose or insulin metabolism, including but not limited to oral or parenteral corticosteroids or topiramate, monoamine oxidase (MAO) inhibitors, growth hormone, oral antidiabetic drugs and insulin within 3 months prior to screening.
- 5. Treatment with antihypertensive medication and statins, unless on stable dose for at least 3 months prior to screening.

- 6. Any weight control treatment, including over-the-counter and herbal medication and supplements, or any medication with a labelled indication for weight loss or weight gain within 3 months prior to screening.
- 7. Any prior treatment with GLP-1 receptor agonists (e.g., exenatide, liraglutide, dulaglutide), dipeptidylpeptidase-4 (DPP-4) inhibitors, oral antidiabetic drugs and insulin.
- 8. Participation in an investigational study within 30 days prior to dosing or 5 half-lives within the last dose of investigational product whichever is longer.
- 9. Calcitonin levels > 20 pg/mL at screening.
- 10. Personal history or current diagnosis of acute or chronic pancreatitis or factors for pancreatitis, such as a history of cholelithiasis (without cholecystectomy) or alcohol abuse.
- 11. History of major depression, anxiety, or other psychiatric disorder (within 2 years of screening), requiring medical treatment, including selective serotonin reuptake inhibitors (SSRIs), serotonin norepinephrine reuptake inhibitors (SNRIs), antipsychotics, lithium. (Use of SSRIs and SNRIs [including bupropion] for reason other than active psychiatric indications [eg, migraine, weight loss, smoking cessation] must meet a 3-month wash-out)
- 12. History of significant suicidal ideation or suicidal behavior/attempts.
- 13. History of any major surgery within 6 months prior to screening.
- 14. History of any serious adverse reaction or hypersensitivity to study drugs components.
- 15. History or current diagnosis of heart disease, defined as symptomatic heart failure (New York Heart Association class III or IV), myocardial infarction, unstable angina requiring medication, transient ischemic attack, cerebral infarct, or cerebral hemorrhage or invasive cardiovascular procedure, such as coronary artery bypass graft surgery (CABG), or angioplasty/percutaneous coronary intervention (PCI) within 6 months of screening. (A diagnostic cardiac catheterization without any intervention does not exclude the subject)
- 16. Cardiac arrhythmia requiring medical or surgical treatment within 6 months prior to screening.
- 17. Personal or family history of medullary thyroid carcinoma (MTC) or a genetic condition that predispose to MTC (ie, multiple endocrine neoplasia type 2).
- 18. Abnormal laboratory results for TSH ($> 1.5 \times ULN \text{ or } < 0.5 \text{ mIU/L}$)
- 19. Abnormal laboratory results for fasting triglycerides \geq 1151 mg/dL (\geq 13.0 mmol/L). Elevated values may be repeated once on a separate day. (Subjects with fasting triglycerides \geq 13.0 mmol/L may be included in the study if LDL< 131 mg/dL (< 3.4 mmol/L) and if they have no history of pancreatitis, CVA, transient

- ischemic stroke, or myocardial infarction as approved per Investigator's discretion.)
- 20. Abnormal laboratory results for LDL >189 mg/dL (>4.9 mmol/L) for untreated dyslipidemia or >158 mg/dL (> 4.1 mmol/L) for treated dyslipidemia. Elevated values may be repeated once on a separate day.
- 21. Clinically significant abnormal hepatic function tests suggestive of hepatic impairment (eg, ALT and AST >2 x ULN).
- 22. Clinically significant abnormal pancreatic function tests suggestive of pancreatic impairment (eg, amylase and lipase >3 x ULN).
- 23. History of renal disease or abnormal kidney function tests at Screening (glomerular filtration rate [GFR] < 60 mL/min/1.73m² as estimated using the MDRD equation).
- 24. History of any active infection, other than mild viral illness within 30 days prior to dosing as judged by the investigator.
- 25. Use of a very-low calorie (1,000 kcal/day) liquid weight loss diet within 6 months prior to screening
- 26. History of alcohol or illicit drug abuse as judged by the Investigator within approximately 1 year.
- 27. Daily use of more than 10 cigarettes/day, or 2 cigars/day, or equivalent use of any tobacco product within 6 weeks prior to Screening.
- 28. Frequent use of marijuana within 6 weeks, or clinically under the effect at screening, as per Investigator evaluation.
- 29. Known history of or positive test for hepatitis B surface antigen (HBsAg), hepatitis C antibody (HCV Ab), or human immunodeficiency virus type 1 (HIV-1) or type 2 (HIV-2) antibody.
- 30. Any anticipated procedures (eg, surgery), that might interfere with the compliance or completion of the study.
- 31. Presence of clinically significant physical, laboratory, or ECG findings (eg, QTcF > 450 msec for males, QTcF > 470 msec for females, LBBB) at screening that, in the opinion of the Investigator, may interfere with any aspect of study conduct or interpretation of results.
- 32. Donation or loss of >500 mL of blood or blood product within 56 days of dosing.
- 33. Mental incapacity, unwillingness or language barriers precluding adequate understanding or cooperation.
- 34. Is employed by Hanmi or ProSciento (permanent, temporary contract worker, or designee responsible for the conduct of the study) or is immediate family of

Hanmi or ProSciento, defined as a spouse, parent, sibling, or child, whether biological or legally adopted.

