- 15. History or current diagnosis of heart disease, defined as symptomatic heart failure (New York Heart Association class III or IV), myocardial infarction, unstable angina requiring medication, transient ischemic attack, cerebral infarct, or cerebral hemorrhage or invasive cardiovascular procedure, such as coronary artery bypass graft surgery (CABG), or angioplasty/percutaneous coronary intervention (PCI) within 6 months of screening. (A

- diagnostic cardiac catheterization without any intervention does not exclude the subject)
- 16. Cardiac arrhythmia requiring medical or surgical treatment within 6 months prior to screening.
- 17. Personal or family history of medullary thyroid carcinoma (MTC) or a genetic condition that predispose to MTC (ie, multiple endocrine neoplasia type 2).
- 18. Abnormal laboratory results for TSH (> 1.5 x ULN or < 0.5 mIU/L)
- 19. Abnormal laboratory results for fasting triglycerides >1151 mg/dL (≥ 13.0 mmol/L). Elevated values may be repeated once on a separate day. (Subjects with fasting triglycerides ≥ 13.0 mmol/L may be included in the study if LDL < 131 mg/dL (< 3.4 mmol/L) and if they have no history of pancreatitis, CVA, transient ischemic stroke, or myocardial infarction as approved per Investigator's discretion.)
- 20. Abnormal laboratory results for LDL 189 mg/dL (>4.9 mmol/L) for untreated dyslipidemia or > 158 mg/dL (> 4.1 mmol/L) for treated dyslipidemia. Elevated values may be repeated once on a separate day.
- 21. Clinically significant abnormal hepatic function tests suggestive of hepatic impairment (eg, ALT and AST >2 x ULN).
- 22. Clinically significant abnormal pancreatic function tests suggestive of pancreatic impairment (eg, amylase and lipase >3 x ULN).
- 23. History of renal disease or abnormal kidney function tests at Screening (glomerular filtration rate [GFR] < 60 mL/min/1.73m² as estimated using the MDRD equation).
- 24. History of any active infection, other than mild viral illness within 30 days prior to dosing as judged by the investigator.
- 25. Use of a very-low calorie (1,000 kcal/day) liquid weight loss diet within 6 months prior to screening
- 26. History of alcohol or illicit drug abuse as judged by the Investigator within approximately 1 year.

	27. Daily use of more than 10 cigarettes/day, or 2 cigars/day, or equivalent use of any tobacco product within 6 weeks prior to Screening.	

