9.1.8 Procedures for Clinical Laboratory Samples

All samples will be collected in accordance with acceptable laboratory procedures. Laboratory samples (Table 9-1) will be taken as described in the Schedule of Events.

Table 9-1 Clinical Laboratory Assessments

Hematology	Serum Chemistry	Urinalysis
CBC with differential:	Hepatic function panel:	Routine urinalysis with
Hematocrit	Alanine aminotransferase	microscopic examination on
Hemoglobin	(ALT/SGPT)	positives(a):
mean corpuscular volume	alkaline phosphatase, serum	Color
(MCV)	aspartate aminotransferase	appearance,
mean corpuscular hemoglobin	(AST/SGOT)	specific gravity
(MCH)	bilirubin, direct	pН
mean corpuscular hemoglobin	bilirubin, total	protein
concentration (MCHC)	protein, total, serum	glucose
red cell distribution width	•	ketones
(RDW)	Renal function panel:	occult blood
percentage and absolute	Albumin, serum	leukocyte esterase
differential counts	BUN	nitrite
platelet count	BUN: creatinine ratio	bilirubin

red cell count (RBC) white blood cell count (WBC)	calcium, serum urobilinogen carbon dioxide, total chloride, serum creatinine, serum glucose, serum phosphorus, serum potassium, serum sodium, serum						
	Lipid panel: Cholesterol, total high-density lipoprotein (HDL) cholesterol low-density lipoprotein (LDL) cholesterol (calculated) triglycerides very low-density lipoprotein (VLDL) cholesterol (calculated)						
	Additional parameters: Amylase Lipase Calcitonin Lactic acid dehydrogenase (LDH) Gamma-Glutamyl Transferase Magnesium Uric Acid						

Diagnostic Screening

Serum/Plasma/Whole Blood	Urine	Breath
HBsAg	Drug Screen Profile	Alcohol breath test at
Anti-HCV	Amphetamines	timepoints stated in the SOE
HIV 1/2	Barbiturates	at the CRU
TSH(b)	Benzodiazepines	
PTT	cocaine (as benzoylecgonine)	
PT	methylenedioxymetamphetamines	
INR	opiates	
HbA1c	Oxycodon	
	phencyclidine (PCP)	
	propoxyphene (Darvon®)	
	tricyclic anti-depressants	
	Urine drug screen as stated in the	
	SOE via commercial kit at the	
	CRU.	
	Female Subjects Only	

Free fatty acid (FFA) C-reactive protein (CRP)

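### Criterion 19 waives the triglyceride exclusion on an LDL value that the protocol obtains only by calculation, which is unreliable or not evaluable at the triglyceride levels where the waiver applies

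*Protocol*

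**What the plan says.** Protocol section 7.2, criterion 19, opens with "Abnormal laboratory results for fasting triglycerides" at or above 1151 mg/dL (13.0 mmol/L) and allows one repeat on another day. The exception follows in parentheses: subjects at or above "13.0 mmol/L may be included in the study if LDL< 131 mg/dL" may enter if they also have no history of pancreatitis, CVA, "ischemic stroke, or myocardial infarction as approved per Investigator's discretion". The synopsis in section 2.0 carries the same exception: "13.0 mmol/L may be included in the study if LDL < 131 mg/dL".

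Section 9.1.8, Table 9-1, lists the lipid panel. Two of its items are "low-density lipoprotein (LDL) cholesterol (calculated") and "very low-density lipoprotein (VLDL) cholesterol (calculated"). No directly measured LDL appears in the table. Below it the protocol adds: "The local laboratory will perform all necessary laboratory tests listed above". Neither the equation nor an upper triglyceride limit for its use is given. The Schedule of Events (Table 16-1) places the lipid panel at screening, so this is the LDL the site will have when it applies criterion 19.

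**The concern.** The exception is used only in subjects with triglycerides of 1151 mg/dL or more. A calculated LDL commonly subtracts a term derived from triglycerides, and in these subjects that term is at its largest. The value meant to justify overriding a triglyceride exclusion then depends heavily on the triglyceride result itself. With cholesterol held fixed, a higher triglyceride result gives a lower calculated LDL and an easier pass.

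At stake is the correctness of an eligibility decision in a first-in-human study. It is taken before dosing, so no later analysis can repair it. Section 7.2 and Table 9-1 together fix a criterion and a measurement method that do not suit each other.

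**Working it through.** **Inputs from the protocol.** Triglyceride (TG) limit 1151 mg/dL (13.0 mmol/L) and LDL limit 131 mg/dL (3.4 mmol/L), both from criterion 19; LDL calculated, from Table 9-1.

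**Assumptions, not in the protocol.** LDL = total cholesterol − HDL − TG/k, with k = 5 (Friedewald form) and a range up to 10; a true VLDL-cholesterol/TG ratio r between 0.10 and 0.22; standard unit factors of 88.57 (TG) and 38.67 (LDL) mg/dL per mmol/L.

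**1. The protocol's own figures.** 13.0 × 88.57 = 1151.4 and 3.4 × 38.67 = 131.5. The paired units agree, so the limits are not misprinted.

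**2. Size of the subtraction and the resulting ceiling.** Write non-HDL for total cholesterol minus HDL. Then LDL < 131 is the same as non-HDL < 131 + TG/k.

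| k | TG/k at TG 1151 | Non-HDL ceiling at TG 1151 | Non-HDL ceiling at TG 2000 |
|---|---|---|---|
| 5 | 230 | 361 | 531 |
| 6 | 192 | 323 | 464 |
| 8 | 144 | 275 | 381 |
| 10 | 115 | 246 | 331 |

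At an ordinary TG of 150 with k = 5, the subtraction is 30 and the ceiling is 161. In the waiver population the subtracted term is close to or above the 131 cut-off for every k in the range.

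**3. Direction at fixed cholesterol.** Take non-HDL = 300 mg/dL.

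- k = 5: calculated LDL is 300 − 230 = 70 at TG 1151, 300 − 300 = 0 at TG 1500, and 300 − 400 = −100 at TG 2000.
- k = 8: the values are 156, 112 and 50. The subject fails at TG 1151 and passes at the higher TG values.

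**4. Error against the true LDL.** Since non-HDL = true LDL + r × TG, calculated LDL = true LDL + TG × (r − 1/k). The condition is met when true LDL < 131 − TG × (r − 1/k). At TG 1151 with k = 5:

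- r = 0.10: 131 + 115 = 246
- r = 0.125: 131 + 86 = 217
- r = 0.15: 131 + 58 = 189
- r = 0.20: 131 (no bias)
- r = 0.22: 131 − 23 = 108

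With k = 8 and r = 0.15 the limit is 131 − 1151 × 0.025 = 102. The error can therefore also work against the subject. For scale, criterion 20 sets its LDL exclusion limits at 189 mg/dL (untreated dyslipidemia) and 158 mg/dL (treated).

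**5. No result reported.** If the laboratory withholds a calculated LDL at these triglyceride values, there is nothing to compare with 131, and the protocol names no substitute.

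**The case against.** The strongest reply is that no equation is named, so the bias is assumed. This stands in part. The downward drift holds at fixed total and HDL cholesterol. Total cholesterol includes VLDL cholesterol and may rise with triglycerides; if it does so at the ratio 1/k there is no bias, and above that ratio the bias reverses. What survives is that, under this form, the LDL result in these subjects depends on a ratio that nobody has measured.

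A reader might infer that the triglyceride exclusion hardly operates. The documents do not support that. The history conditions and investigator approval apply as well. Criterion 22 covers clinically significant abnormal pancreatic tests, and criterion 31 covers clinically significant laboratory findings that the investigator thinks may interfere with the study. If LDL is not reported, the natural reading is that the condition is unmet and the subject stays out, which is conservative.

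A reader might also see a conflict with criterion 10. Its wording, "factors for pancreatitis, such as a history of cholelithiasis (without cholecystectomy) or alcohol abuse", does not name triglycerides, and criterion 19 is the specific rule for them, so no contradiction is shown.

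Nor can one say how many such subjects would enter a cohort, or that they would distort amylase and lipase: the protocol gives no prevalence, and both enzymes are measured at screening and on Day -1.

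Finally, LDL and VLDL are also pharmacodynamic endpoints, but exploratory and summarised descriptively. For an assumed 30% triglyceride fall from 150 mg/dL, the artefact in LDL at k = 5 is only 0.30 × 150 × (0.20 − r), or 2 to 5 mg/dL for r of 0.15 to 0.10. That does not add to the point.

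**Conclusion.** The point holds for the LDL part of the criterion 19 exception and no further. The protocol specifies a calculated LDL for a decision taken only at triglycerides of 1151 mg/dL or more. There, for k between 10 and 5, the subtracted term is 115 to 230 mg/dL against a cut-off of 131. With k = 5, the true LDL that would pass runs from about 246 mg/dL (r = 0.10) through 189 (r = 0.15) to 131 (r = 0.20), and falls to 108 at r = 0.22. These figures rest on the assumed form of the equation and on the assumed ratios. If no value is reported, the condition cannot be evaluated. The exclusion as a whole still operates through its other gates. This is a mismatch between two sections that is worth correcting, likely to touch few subjects; it is not a flaw in the study design.

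**What to change.** Reconcile criterion 19 (section 7.2 and the synopsis in section 2.0) with Table 9-1. State that the LDL used for this exception is directly measured on the same screening sample, and add that test to Table 9-1. State the calculation method and the triglyceride range in which the calculated LDL is valid. The laboratory should confirm that its direct method is itself usable at these triglyceride values, which the documents do not address. The triglyceride and LDL limits themselves need not change for this purpose.

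The cost is a reflex assay for very few subjects and a few amended lines. A few candidates who would have passed on a calculated LDL may no longer qualify; where the calculation errs upward, some may newly do so.
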